11.1.1 Adverse Events Leading to Discontinuation of Study Drug

A summary of incidence rates (frequencies and percentages) of TEAEs leading to discontinuation of study drug by treatment group, SOC, and preferred term will be prepared for the Safety population.

A data listing of AEs leading to discontinuation of study drug will also be provided, displaying details of the event(s) captured on the CRF.

11.1.2 Serious Adverse Events

A summary of incidence rates (frequencies and percentages) of serious adverse events (SAE) by treatment group, SOC, and preferred term will be prepared for the Safety population. A data listing of SAEs will also be provided, displaying details of the event(s) captured on the CRF.

11.1.3 Oral TEAEs

In light of the study drug’s sublingual route of delivery, subjects will undergo a detailed examination of the oral cavity at screening and brief examinations at all other visits.

AEs involving the oral cavity may be spontaneously reported by the subject, observed during an oral cavity examination, or both. Oral cavity AEs will be identified by a “yes” response to the CRF question, “Is the AE in the oral cavity?” Additional information will be collected on oral cavity AEs (based on a “yes” response to the above question), including whether the AE occurs immediately or very soon after dosing, an approximation of the duration of the AE (less than or greater than 60 minutes), and whether the AE is still present the next morning upon awakening.

A separate by-subject listing of oral cavity AEs (including pre-treatment oral cavity AEs) will be provided.

11.1.4 Deaths

A listing of deaths will also be provided for the Safety Population.

11.2 Clinical Laboratory Evaluations

Laboratory data (analytes for Chemistry and Hematology) will be summarized by treatment and visit for the Safety Population. Descriptive summaries of actual values and changes from baseline will be presented by study visit and last available assessment for each clinical laboratory analyte and each treatment group. 95% confidence intervals will be presented for change from baseline. ET data will be analyzed with the closest visit that does not have a valid assessment value.

Laboratory values will be displayed in the data listings with their corresponding normal ranges, and those values that are outside the normal range will be flagged. For each laboratory analyte, shifts in assessments of abnormality from baseline to each scheduled time point will be presented in shift tables.

A by-subject listing of all clinical laboratory (Chemistry, Hematology and Urinalysis) data will

also be provided.

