11.5.2. Early Termination (Post-Randomization)

In accordance with the Declaration of Helsinki, patients have the right to withdraw from the study at any time for any reason, and they will be advised of this right. The Investigator and Tonix also have the right to remove patients from the study. Specific reasons for removal of a patient from the study could include, but are not limited to:

- An AE
- An illness that, in the judgment of the Investigator or Tonix, might invalidate the study data or place the patient at risk
- The request of the patient, Investigator, or Tonix, whether for administrative or other reasons
- Pregnancy

Patients who wish to terminate their participation in the study should be instructed to come to the clinic for an Early Termination Visit. The purpose of the Early Termination visit is to obtain critical information about the patient's participation and should be scheduled preferably before there has been a substantial lapse in study drug usage. However, even if there has been a drug lapse, the patient should be encouraged to return to the clinic for this visit and should be instructed to return all study drug and bottles. NOTE: These visit procedures are not intended for patients who fail to qualify for randomization or for patients who withdraw from the study prior to receipt of a dose of double-blind study drug.

The following assessments and procedures are completed at this visit as ordered below:

- Document reason for early termination
- Assess changes in medication history and concomitant medications
- Assess study drug compliance (Telephone visit exception - patient will be instructed to count the number of tablets remaining in their current bottles, document this on a patient provided form, and return this form with the study drug (including bottles) to the site for assessment of compliance in a pre-paid pre-addressed courier envelope supplied in a "tele-visit" package to patient).
- Have patient complete the BDI-II
- Administer the "Since Last Visit" version of the C-SSRS
 - a. Results of the C-SSRS and BDI-II should be reviewed together to ensure (1) the patient is not experiencing suicidal ideation or worsening depression that requires intervention and (2) both scales are providing a consistent clinical picture of the patient with regard to suicidality. (Telephone visit exception – response to Question #9 of the BDI-II is reviewed with the patient and C-SSRS is administered over the phone).

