13.5. Safety Analyses

Safety analyses will be performed using the Safety Population. The analysis of safety assessments in this study will include summaries of the following safety and tolerability data collected for each patient:

- Incidence of Adverse Events
- Changes from baseline in clinical laboratory tests
- Changes from baseline in vital signs
- Changes from baseline in physical examination findings including examination of the oral cavity
- Monitoring suicidality using the C-SSRS
- Changes from baseline in BDI-II scores

All AEs, treatment-emergent adverse events (TEAE), and serious adverse events (SAE) will be coded using the MedDRA.

An AE summary table will be presented for the following:

- All TEAEs
- TEAEs by severity
- TEAEs leading to study drug discontinuation
- TEAEs by relationship
- SAEs
- Oral cavity TEAEs
- Oral cavity TEAEs by severity

Summaries of incidence rates (frequencies and percentages), of individual AEs by MedDRA SOC and preferred term will be prepared. Such summaries will be displayed for all TEAEs, oral cavity TEAEs, TEAEs by maximum severity, and TEAEs by strongest relationship to study drug.

Each patient will be counted only once within each summation level (SOC; preferred term). If a patient experiences more than one TEAE within each summation level, the TEAE with the strongest relationship or the maximum severity, as appropriate, will be included in the summaries of relationship and severity.

In the AE data listings, all AEs will be displayed.

Laboratory data include analytes for Chemistry and Hematology, and these will be summarized by treatment and visit for the Safety Population. Descriptive summaries of actual values and changes from baseline will be presented by study visit and last on-treatment assessment for each clinical laboratory analyte and each treatment group. 95% confidence intervals will be presented for change from baseline.

Laboratory values will be displayed in the data listings with their corresponding normal ranges, and those values that are outside the normal range will be flagged. For each laboratory analyte, shifts in assessments of abnormality from baseline to each scheduled time point will be presented in shift tables.

A by-patient listing of all clinical laboratory data will also be provided.

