Descriptive summaries (mean, SD, median, minimum, and maximum) of actual values and changes from baseline at each assessment time point and last on-treatment assessment will be calculated for vital signs including weight, BMI, body temperature, pulse rate, systolic blood pressure and diastolic blood pressure. 95% confidence intervals will be presented for change from baseline.

Based on the C-SSRS results, the overall number of patients with lifetime and/or current suicidal ideation (by item and category), suicidal behavior (by item and category), or self-injurious behavior at the screening and baseline visit will be summarized by visit and treatment group. Additionally, the overall number of patients with any suicidal ideation or behavior (by type and in total) or self-injurious behavior while on-treatment will be provided by treatment group. Patients will only be counted once for on-treatment at the worst-case response for each item.

Physical examination data and oral examination data will be presented in data listings.

Descriptive summaries (mean, SD, median, minimum, and maximum) of actual values and changes from baseline at each assessment time point and last on-treatment assessment will be calculated for BDI-II scores. 95% confidence intervals will be presented for change from baseline.

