8.1.2 Data Handling for Subjects Who Withdraw/Drop Out from the Study

Subjects who withdraw/drop out from the study will have the early termination (ET) data collected at their ET visit included in the analysis at the closest visit (Week 2, 6, 10, 14), using midpoints between visits to window the early termination. If this results in two records for a given visit, then the one closest to the targeted date will be used.

For example, a subject with valid Week 10 clinic assessment collected on Day 72 that has early termination data collected on Day 79, would have the early termination data mapped to Week 10; however, since Day 72 data is present and closer to the target date, it would be analyzed and the Day 79 data would be excluded. A subject without valid Week 10 data who early terminates on Day 79 would have the Day 79 data analyzed with the Week 10 data.

Subjects who provide 14 weeks of diary pain data will be analyzed as completers for purposes of the primary analysis, even if for some reason they are unable to attend a Week 14 final study visit. As a specific example, a subject who successfully provides 14 weeks of diary data as described in [Section 8.2.1](#), but who is unable to attend a final study visit during the required time window because of travel or other circumstances, would be analyzed as a completer for purposes of the primary endpoint, but would be missing non-diary based secondary outcome measures at

the Week 14 endpoint. For safety data, the last observation available will be summarized in addition to the presentation above (grouping ET visits with the closest planned visit); this will combine the ET visit data with the completers' Week 14 data, regardless of when the ET occurred.

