11.4 Vital Signs

Descriptive summaries (mean, SD, median, minimum, and maximum) of actual values and changes from baseline at each assessment time point and last available assessment will be calculated for vital signs including weight, BMI, body temperature, pulse rate, systolic blood pressure and diastolic blood pressure. 95% confidence intervals will be presented for change from baseline.

These summaries will be presented by treatment and assessment time for the Safety population. ET data will be analyzed with the closest visit that does not have a valid assessment value.

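### The SAP replaces the protocol's last on-treatment summary of laboratory values and vital signs with a last-available one, without declaring it, so values taken off drug can enter the end-of-study line

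*SAP*

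**What the plan says.** Protocol 13.5 and the SAP describe the same descriptive line: actual values and change from baseline, with 95% confidence intervals for the change. They differ on which value represents the end of study.

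- Laboratory values. Protocol 13.5: "will be presented by study visit and last on-treatment assessment for each clinical laboratory analyte and each treatment group". SAP 11.2: "Descriptive summaries of actual values and changes from baseline will be presented by study visit and last available assessment for each clinical laboratory analyte".
- Vital signs. Protocol 13.5: "changes from baseline at each assessment time point and last on-treatment assessment will be calculated for vital signs". SAP 11.4: "at each assessment time point and last available assessment will be calculated for vital signs".
- BDI-II. Protocol 13.5 uses the last on-treatment value here too. SAP 11 lists BDI-II among the safety data but has no subsection that analyses it.

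SAP 8.1.2 gives a general rule in line with 11.2 and 11.4. The last safety observation is summarised, and ET data are combined with completers' Week 14 data "regardless of when the ET occurred". It sets no condition on time since the last dose.

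On the ET visit, Protocol 11.5.2 prefers a date before any substantial lapse in study drug, and then adds that "even if there has been a drug lapse, the patient should be encouraged to return to the clinic for this visit".

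SAP 13 lists one change from the protocol, the addition of the in-clinic pain assessments. It does not mention the last-assessment rule.

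**The concern.** An on-treatment summary describes patients while exposed to the drug. A last-available summary mixes in values from patients who have already stopped. If an effect on pulse, blood pressure or weight fades off drug, those values move the active-arm mean change toward placebo. The patients concerned stopped early, some of them because of adverse events.

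Vital signs carry weight in this trial. The ECG is scheduled at Screening only (Protocol Table 2), so pulse and blood pressure are the only scheduled post-dose cardiovascular measurements. The appended label for the reference product (section 6.2) lists tachycardia, hypotension, hypertension and weight change among reported reactions.

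The change also departs from the protocol's safety analysis without being declared, so a reader of the study report could take the SAP line for the one the protocol promised.

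**Working it through.** **Step 1. Do the two rules select different values?** They agree for a patient whose last visit falls directly after the last dose. They differ only when the last value follows a lapse. Protocol 11.5.2 allows such visits, and SAP 8.1.2, 11.2 and 11.4 contain nothing that keeps the values out.

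**Step 2. What would the on-treatment rule use instead?**

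- Vital signs are scheduled at every visit, except that telephone visits collect none. A patient with a post-lapse ET value will usually have an earlier on-treatment value to take its place.
- Laboratory tests are scheduled at Screening and Week 14/ET only. A patient whose single post-baseline draw follows a lapse has no earlier one, so an on-treatment rule drops that patient.

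**Step 3. Size for vital signs.** The plan gives no figure to reproduce. For illustration:

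- f = share of active-arm patients whose last value follows a lapse (assumed; not in the documents).
- t = lapse in days (assumed; not in the documents).
- Half-life 32 h, range 8-37 h, from section 12.3 of the appended label. It belongs to the oral extended-release product, not to TNX-102 SL.
- Effect proportional to remaining drug (assumed).

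Residual r = 2^(-24t/32). Relative shrinkage of the mean effect = f × (1 - r).

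At t = 2, r = 2^(-1.5) = 0.354. At t = 7, r = 2^(-5.25) = 0.026.

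| f | 2-day lapse | 7-day lapse | Ceiling (full washout) |
|---|---|---|---|
| 2% | 1.3% | 1.9% | 2% |
| 5% | 3.2% | 4.9% | 5% |
| 10% | 6.5% | 9.7% | 10% |
| 20% | 12.9% | 19.5% | 20% |

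For example, 0.20 × (1 - 0.354) = 12.9%. Across the label's half-life range, r after 2 days runs from 0.016 (8 h) to 0.407 (37 h), so at f = 10% the shrinkage runs from 10 × (1 - 0.407) = 5.9% to 10 × (1 - 0.016) = 9.8%. Whatever the half-life, the ceiling is f.

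**Step 4. Direction for laboratory values.** Set the mean on-drug effect in patients without a lapse to 1, and let k be the on-drug effect in lapsed patients relative to it. Last available gives (1 - f) + f × k × r. The on-treatment rule, which drops the lapsed patients, gives 1. Last available is the smaller of the two only if k × r < 1, that is k < 1/r. The break-even k is 1.68 after 1 day, 2.83 after 2 days and 4.76 after 3 days.

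With f = 10% and a 2-day lapse:

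- k = 2: last available 0.9 + 0.1 × 2 × 0.354 = 0.971; on-treatment 1; all patients measured on drug 0.9 + 0.1 × 2 = 1.1.
- k = 3: last available 0.9 + 0.1 × 3 × 0.354 = 1.006; on-treatment 1; all measured on drug 0.9 + 0.1 × 3 = 1.2.

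Both rules understate the on-drug effect when early stoppers are the more affected patients, and which one understates it more depends on k. That is a reason to show both lines.

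**The case against.** The strongest reply is that this is a wording difference in a descriptive table. Protocol 13 leaves the complete analysis description to the SAP, and the protocol never defines on-treatment. By-visit tables, laboratory shift tables, adverse event tables and listings are all provided. Protocol 11.5.2 asks for the ET visit before a substantial lapse, so long lapses need not be common, and a telephone ET yields neither laboratory values nor vital signs. All of this stands, and it limits the size. It does not explain why the SAP changed the protocol's rule or left the change out of SAP 13.

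A reader might infer more than the documents support:

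- *That SAP 8.1.2 pools ET values whatever the gap since the last dose.* In context the phrase contrasts with grouping ET visits by closest planned visit, so it refers to the study week. The SAP is silent on the gap. That silence is enough for the point, but it is not a stated rule.
- *That a patient with no post-dose laboratory value would carry the Screening value forward as a change of zero.* SAP 8.1 defines change as a post-baseline value minus baseline, and SAP 8.1.3 imputes no missing safety data. Such a patient has no change score.
- *That this is the only line combining all patients at the end of treatment.* For laboratory values it is not. SAP 11.2 also places ET values in the by-visit tables, at the closest visit without a valid value. If only scheduled laboratory visits count, that is Week 14. Adding an on-treatment line leaves those by-visit rows as they are.
- *That the SAP rule necessarily hides laboratory effects.* Step 4 shows that the direction is open.
- *That a firm dilution percentage follows from a plausible dropout rate.* The documents give neither dropout, nor ET attendance, nor lapse length, and the half-life is that of another formulation.

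**Conclusion.** The point holds in a limited form. The protocol and SAP conflict on the end-of-study value for laboratory tests and vital signs, the SAP leaves the BDI-II line unspecified, and SAP 13 does not declare the change. These findings rest on the text alone.

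For vital signs, the SAP rule can bias a reversible effect toward zero. The bias cannot exceed the share of active-arm patients whose last value follows a lapse. It is about 1-20% of the effect if that share is 2-20% and lapses last 2-7 days, with effect proportional to drug level and the 32 h half-life. Patients without a lapse contribute nothing to it, and effects that do not reverse off drug are not diluted. For laboratory values no direction can be claimed. No efficacy conclusion or formal test is affected.

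**What to change.** 1. In SAP 11.2 and 11.4, add the protocol's last on-treatment line. Define it as the last value after the first dose and within a stated short lag after the last dose. The lag must still keep a Visit 6 held the day after the final bedtime dose (Day 99 after a Day 98 dose).
2. Add a BDI-II analysis subsection under SAP 11 with the same line.
3. Keep last available as a second line, restricted explicitly to post-baseline values.
4. Align the last sentence of SAP 8.1.2, so that pooling ET with Week 14 data describes the last-available line only and the on-treatment line has its own rule.
5. List the addition, with the definition of the lag, in SAP 13.

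The cost is small. SAP 12.3 already uses first and last dose dates from the CRF, so this is one date filter and one extra table row per parameter. The on-treatment line will have a slightly smaller n, mostly for laboratory values, and the second line keeps those patients visible.

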11.3 Columbia Suicide Severity Rating Scale (C-SSRS)

The C-SSRS is an instrument that measures suicidal ideation and behavior, as represented by the items displayed in the table below. Frequency counts of yes/no responses to each item, and whether any suicidal ideation or behavior is present, will be summarized as described below.

The overall number of subjects with lifetime and/or current suicidal ideation (by item and category), suicidal behavior (by item and category), or self-injurious non-suicidal behavior at the screening and baseline visit will be summarized by visit and treatment group.

Additionally, the number of subjects with increase over baseline in suicidal ideation at any time point will be reported. The maximum ideation across all visits for a subject will also be summarized with counts and percentages both for all subjects and among subjects with an increase in ideation. Likewise, the count and percentage of subjects with any suicidal behavior will be reported along with a summary of the most extreme behavior each subject reported.

| Category | Items |
|----------------------|---|
| A) Suicidal Ideation | (1) Wish to be dead (2) Non-specific active suicidal thoughts (3) Active suicidal ideation with any methods (not plan) without intent to act (4) Active suicidal ideation with any some intent to act, without specific plan (5) Active suicidal ideation with specific plan and intent |
| B) Suicidal Behavior | (6) Preparatory acts or behavior (7) Aborted attempt (8) Interrupted attempt (9) Actual attempt (10) Completed suicide Suicidal Behavior present (composite of items 6-10) Non-Suicidal Self-Injurious Behavior |

A data listing of C-SSRS results will include only subjects with suicidal ideation, suicidal behavior, or self-injurious behavior without suicidal intent at any visit. For subjects with suicidal ideation, suicidal behavior, or self-injurious behavior without suicidal intent at any time, data from all visits will be displayed.

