The primary ITT analysis will provide the following causal estimand for the primary analysis: the difference in the weekly mean change from Baseline of the daily patient self-reported 24-hour recall average pain severity rating using an 11-point (0-10) NRS evaluated at the Week 14 endpoint in all randomized patients attributable to the initially randomized treatment assignment. The primary analysis will use a Mixed Model Repeated Measures (MMRM) approach with multiple imputation for missing data. Covariates in the model will include the fixed categorical effects of treatment, center, study week, and treatment by study week interaction, as well as the continuous fixed covariates of baseline score and baseline score by study week interaction. Please see the separate Statistical Analysis Plan (SAP) for more details on the primary and secondary analyses.

Safety Analyses:

Adverse events will be coded using the Medical Dictionary for Regulatory Activities (MedDRA) and will be summarized overall and by preferred term and system organ class. Adverse events will also be summarized by severity and relationship to study drug. Serious AEs, AEs involving the oral cavity and AEs leading to discontinuation of study drug will also be summarized. Actual values and changes from baseline for clinical laboratory test results and vital signs will be summarized using descriptive statistics (n, mean, SD, median, minimum, and maximum). The number of patients with baseline and treatment-emergent suicidal ideation and/or suicidal behavior or self-injurious behavior, based on the C-SSRS, will be summarized by treatment group.

Sample Size:

The study is planned to enroll approximately 470 patients total in a 1:1 randomization; that is, 235 patients in each of the TNX-102 SL and placebo arms. [REDACTED]

Pharmacogenomic Analyses

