12.3.4. Columbia- Suicide Severity Rating Scale (C-SSRS)

The C-SSRS is a questionnaire developed by researchers at Columbia University to assess and track suicide risk and behavior. This scale is intended to be used by individuals who have received training in its administration. The questions contained in the Columbia-Suicide Severity Rating Scale are suggested probes. Ultimately, the determination of the presence of suicidal ideation or behavior depends on the judgment of the individual administering the scale.

Two versions of this questionnaire will be utilized in this study. At Visit 1, the "Baseline/Screening" questionnaire will be administered, and the recall periods will be "lifetime" and "within the past 6 months" for suicidal ideation and "within the past 1 year" for suicidal behavior. Patients whose responses are indicative of suicidal ideation with intent and/or plan (e.g., Type 3, 4 or 5 suicidal ideation) within the past 6 months or a history of suicidal behavior within the past year will be excluded from participation, with recommended referral for appropriate intervention.

At all subsequent visits (Visits 2, 3, 4, 5 and 6), the "Since Last Visit" version of the questionnaire will be administered, and the recall period on this will be "since the last visit". Note that if there has been a significant change in responses indicative of increased suicide risk, appropriate intervention should be prescribed.

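### SAP 11.3 takes each subject's maximum C-SSRS ideation over all visits, without the on-treatment limit that Protocol 13.5 requires

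*SAP*

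**What the plan says.** **Protocol.** Section 13.5 asks for two separate C-SSRS summaries. The first describes lifetime and/or current status at screening and baseline. The second is limited to treatment: "Additionally, the overall number of patients with any suicidal ideation or behavior (by type and in total) or self-injurious behavior while on-treatment", given by treatment group, with the counting rule "Patients will only be counted once for on-treatment at the worst-case response for each item". The Synopsis makes the same split: "The number of patients with baseline and treatment-emergent suicidal ideation and/or suicidal behavior or self-injurious behavior".

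**SAP.** Section 11.3 keeps the screening/baseline summary. In place of the on-treatment summary it specifies:

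- a count of subjects whose ideation increases over baseline at any time point;
- for ideation, "The maximum ideation across all visits for a subject will also be summarized with counts and percentages", shown for all subjects and again among those with an increase;
- for behavior, "the count and percentage of subjects with any suicidal behavior will be reported along with a summary of the most extreme behavior" each subject reported, with no time window.

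The on-treatment restriction does not appear in Section 11.3, and no on-treatment summary of self-injurious behavior is specified. Section 13, which lists changes from the planned analysis, names only the in-clinic pain assessments.

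**The instrument.** Under Protocol 12.3.4, the Visit 1 form recalls ideation over the lifetime and the past 6 months, and behavior over the past year. Visits 2 to 6 use the Since Last Visit form.

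**The concern.** The Visit 1 form and the later forms cover different periods. A maximum taken over both can be set by something that happened years before randomisation, which treatment cannot influence. In a safety table comparing arms, such history adds a similar background to each arm and pulls the ratio between them towards 1. It can also replace a subject's on-treatment category with a more severe historical one.

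At stake is the by-type, worst-case, on-treatment ideation table that the protocol promises for a centrally acting drug. As the SAP is worded, a programmer could follow it exactly and not produce that table.

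**Working it through.** The documents give no figure to reproduce, so the check is a comparison of texts followed by an illustration of scale.

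**Step 1: do the visits include Screening?** The C-SSRS is administered at Visit 1 (Protocol Table 2, 11.1.4 and 12.3.4). SAP 11.3 sets no post-dose limit on the maximum. SAP 11.5 describes oral examinations at each visit and spells that out as Screening through Week 14. The literal reading therefore includes Visit 1.

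**Step 2: can pre-treatment ideation be present in a randomised patient?** Protocol 8.3 (criterion 5) and 12.3.4 exclude Type 3-5 ideation in the past 6 months. Section 11.1.4 names only Types 4 and 5 for that period. None of these rules excludes older severe ideation. What enters the maximum depends on the Screening column used:

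- Lifetime column: Types 1-5 can enter.
- 6-month column only: mainly Types 1-2 can enter, because recent severe ideation is excluded.

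The SAP does not say which column is used.

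**Step 3: does restricting to subjects with an increase solve it?** No. SAP 8.1 defines baseline as the last value before first dose, normally the Visit 2 Since Last Visit form. Take a subject with lifetime Type 5, nothing at Visit 2, and Type 1 on treatment. The subject counts as an increase, and the maximum over all visits is still Type 5. The protocol's table would show Type 1.

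**Step 4: scale, for ideation of any type.** The only input from the documents is 235 per arm (Protocol 13.2). Let L be the share with history that feeds the maximum, equal in both arms, and p the on-treatment rate, independent of history. Both are assumptions. The share counted is L + (1 − L)p.

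With p = 1% on placebo and 4% on active:

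| L | Placebo | Active | Ratio |
|---|---|---|---|
| 0% (on-treatment only) | 235 × 0.010 = 2.4 | 235 × 0.040 = 9.4 | 4.0 |
| 10% | 235 × 0.109 = 25.6 | 235 × 0.136 = 32.0 | 1.25 |
| 20% | 235 × 0.208 = 48.9 | 235 × 0.232 = 54.5 | 1.12 |
| 30% | 235 × 0.307 = 72.1 | 235 × 0.328 = 77.1 | 1.07 |

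History makes up 0.10/0.136 = 74% of the active-arm count at L = 10%, and 0.30/0.328 = 91% at L = 30%. With 2% versus 6% on treatment, the ratio falls from 3.0 to 1.31, 1.15 and 1.09. If on-treatment ideation is more common in patients with a history, the dilution is greater than shown.

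**Step 5: behavior.** Protocol 12.3.4 gives a 1-year recall at Screening. Behavior in that year is exclusionary (8.3, 11.1.4, 12.3.4), and behavior between Screening and Baseline leads to screen failure (8.3, 11.2.2). On that reading L is close to zero for behavior, so the illustration does not carry over to the behavior row.

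**The case against.** **The order of the paragraphs suggests follow-up visits.** SAP 11.3 first gives lifetime and current data their own table, and only then turns to increases and maxima. A sensible programmer could take the visits to mean those after baseline. The ambiguity is real, so a reader who infers that the SAP definitely feeds lifetime answers into the maximum goes too far: no sentence says so. But no sentence rules it out either, and the on-treatment wording that would settle it has been dropped.

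**The behavior table.** A reader might infer that old suicidal behavior is carried into the behavior row in the same way. The documents do not support this. The all-visits wording is attached to ideation only, and the behavior sentence merely follows with a linking word: "Likewise, the count and percentage of subjects with any suicidal behavior will be reported along with a summary of the most extreme behavior each subject". The 1-year recall and the exclusions leave almost nothing to carry over. The one contrary sign is that the screening/baseline summary mentions lifetime status in a sentence that also covers behavior, and it is unclear whether lifetime applies to both. What stands is that the behavior summary has no stated window, which departs from Protocol 13.5 even if contamination is slight.

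**Other outputs show on-treatment events.** The increase-over-baseline count captures emergent ideation. The listing shows every visit for any subject with ideation or behavior. Under Protocol 14.3, Type 4-5 ideation after consent is always an SAE and Type 3 an AE, and SAP 11.1 tabulates these. So it would be wrong to infer that on-treatment events disappear from the report. However, none of these outputs is a by-type on-treatment worst case, Section 14.3 sets no such rule for Types 1-2, and the increase count has no counterpart for behavior.

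**The tables are descriptive.** No test is planned on them, and no endpoint or error rate depends on them. This is correct and limits the weight of the point.

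**Conclusion.** The discrepancy holds for ideation. Protocol 13.5 requires an on-treatment worst case, SAP 11.3 states a different rule, and the change is not declared. Followed literally, the rule mixes pre-treatment ideation into the maximum, including among subjects with an increase.

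How much this matters depends on two things the documents do not give: which Screening recall column is used, and how common past ideation is among those randomised. Under the assumed rates, a fourfold on-treatment ratio shrinks to between 1.25 and 1.07 for lifetime history of 10% to 30%. With the 6-month column alone, the severe rows would be largely unaffected.

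For behavior, the finding is only that the window is missing; contamination is uncertain and probably small. The trial's alpha, power and efficacy conclusions are untouched. This should be corrected, but it does not threaten the trial.

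**What to change.** In SAP 11.3:

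- Limit the maximum-ideation summaries (all subjects, and those with an increase) and the any/most-extreme-behavior summary to Since Last Visit assessments after the first dose: Visits 3 to 6 or Early Termination, and unscheduled assessments.
- Present them by treatment group, with each subject counted once per item at the worst on-treatment response.
- Add on-treatment self-injurious behavior, which Protocol 13.5 requires: "or self-injurious behavior while on-treatment will be provided by treatment group".
- Keep lifetime and recent history in the existing screening/baseline table only.

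If the sponsor also wants a maximum over all visits, it should be labelled as including history, name the Screening recall column used, and be listed in SAP Section 13.

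The cost is a few lines of SAP text, a visit filter in the table program and one added row for self-injury. No new data are needed.
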